## Cycle 1 - Day 1 Procedures

- Review of change in concomitant medication
- AE recording

20		PRIVILEGED & CONFIDENTIAL
Investigational Product: AGI-134	A Phase I/IIa, multicentre, two-parts, open label study designed to evaluate the safety and tolerability of escalating	Protocol No. AGI-134.FIM.101
Phase: I/IIa		Version 6.1 31 May 2021

#### ECG assessment:

- A 12-lead ECG Holter recording device will be connected to the subject 1-2 hours prior to AGI-134 administration and record ECG consecutively for at least 24 hours post AGI-134 administration.
- ECG printouts for safety assessment will be extracted prior to AGI-134 administration (up to 1 hour before dose) and 2 hours post dose (± 30 minutes).
- Symptom-directed physical examination pre-dose only
- Examination of injection- site will be performed 1 hour (±30 min) pre-AGI-134 administration, 1 hour (±30 min)
- Vital signs will be performed up to 1 hour pre-AGI-134 administration and 0.5, 1, 24, 36, 48 and 72 hrs post AGI-134 administration.
- ECOG performance status
- Photography of superficial injected and non-injected lesions will be performed 1 hour pre-AGI-134 administration (±30 min), 1 hour (±30 min)
- Review general instructions before study drug administration (see section 5.7)
- AGI-134 administration on Day 1
- Blood will be drawn for:
  - o CH50 pre-dose
  - o C5a pre-dose, 2 and 6 hours post AGI-134 administration
  - o Flow cytometry pre-dose and 24 hours post AGI-134 administration
  - O Cytokines pre-dose, 2, 6, 12 and 24 hours post AGI-134 administration
  - Anti-Gal antibodies IgG/IgM and sub classing pre-dose
  - PBMC isolation + cryopreservation pre-dose
  - Human leukocyte antigen (HLA) and MHCII haplotyping pre-dose
  - DNA isolation (MSI/dMMR/TMB, WES) pre-dose
  - TCR Sequencing pre-dose
  - RNA isolation (Gene expression/sequencing) pre-dose
  - PK of AGI-134 and metabolites: up to 1 hour prior to AGI-134 administration and at 0.5, 1, 2, 4, 6, 8, 12, 24, 36, 48 and 72 hrs post AGI-134 administration.
     For detailed time window for sample collection refer to the Laboratory Manual.

## 5.3.2 Cycle 1 - Day 3

- Blood will be drawn for:
  - o CBC with differential 48-72 hrs post AGI-134 administration
  - o Biochemistry Panel 48-72 hrs post AGI-134 administration
  - Cytokines: 48hrs post AGI-134 administration
  - RNA isolation (Gene expression/sequencing) 48±24hrs post AGI-134 administration
  - o PBMC isolation + cryopreservation: 48 ±24 hrs post AGI-134 administration

agalin A subsidiary of Bio	nnune DLINERX	PRIVILEGED & CONFIDENTIAL
Investigational Product: AGI-134		Protocol No. AGI-134.FIM.101
Phase: I/IIa		Version 6.1 31 May 2021

- Photography of superficial injected lesions prior to tumour tissue biopsy, if applicable
- Examination of injection prior to tumour tissue biopsy, if applicable
- Tumour tissue biopsy will be performed 48 ±24 hrs post AGI-134 administration, from injected lesions only. This biopsy is mandatory for superficial injected lesion and is also requested for deep lesions, unless it is not considered in the best interest for the patient by the PI.

## 5.3.3 Cycle 1 - Day 8 and Day 15

The following procedures will be performed:

- Review of change in concomitant medication
- AE Recordings
- Symptom-directed physical examination
- Examination of injection site
- Photography of superficial injected and non-injected lesions if applicable
- Vital signs (blood pressures, pulse rate, O2 saturation, oral temperature in °C, respiratory rate)
- Blood will be drawn for:
  - CBC with differential
  - Biochemistry panel
  - o Anti-Gal antibodies IgG/IgM (Cycle 1 Day 8 only)

## 5.3.4 Cycles 2, 3 and 4

AGI-134 will be administered on Day 1 of each cycle. The following procedures will be performed during these visits; each assessment should be performed before administration of the investigational product unless otherwise specified. Detailed activities are presented in the SoA (APPENDIX A).

#### Cycle 2 Procedures

- Review concomitant medications
- AE Recording
- A 12-lead ECG will be recorded prior to AGI-134 administration (up to 1 hour before dose) and 2 hours post dose (± 30 minutes).
- Symptom-directed physical examination pre-dose only
- Examination of injection site will be performed 1 hour (±30 min) pre-AGI-134 administration and 1 hour (±30 min) post AGI-134 administration
- Vital signs (blood pressures, pulse rate, O2 saturation, oral temperature in °C, respiratory rate) will be assessed pre-dose and 2 hours post dose
- ECOG performance status
- Photography of superficial injected and non-injected lesions, (if a different lesion is injected the previous injected lesion should be photographed as well): 1 hour (±30 min) pre-AGI-134 administration and 1 hour (±30 min) post AGI-134 administration

Protocol AGI-134.FIM.101 CONFIDENTIAL Page 47 of 108

agalin A subsidiary of BIO		PRIVILEGED & CONFIDENTIAL
Investigational Product: AGI-134		Protocol No. AGI-134.FIM.101
Phase: I/IIa	doses of AGI-134 in unresectable/metastatic solid tumours.	Version 6.1 31 May 2021

- Review general instructions before study drug administration (see section 5.7)
- AGI-134 administration (every effort should be made to inject the same lesion as in previous cycle)
- Urinalysis
- · Pregnancy test in urine
- · Blood will be drawn for:
  - Disease markers according to subject's disease
  - o PT/INR and aPTT (results should be available before injection)
  - CBC with differential
  - o Biochemistry panel
  - o T3, free T4 and TSH
  - o C5a pre-dose and 2 hours post AGI-134 administration
  - o Flow cytometry pre-dose only
  - o PBMCs Isolation + Cryopreservation pre-dose only
  - Anti-Gal antibodies IgG/IgM and sub classing pre-dose only
  - PK of AGI-134 and metabolites: up to 1 hour prior to AGI-134 administration and 2 hours post dose

## **Cycle 3 Procedures**

- · Review concomitant medications
- AE Recording
- ECG assessment:
  - A 12-lead ECG Holter recording device will be connected to the subject 1-2 hours prior to AGI-134 administration and record ECG consecutively for at least 24 hours post AGI-134 administration.
  - o ECG printouts for safety assessment will be extracted prior to AGI-134 administration (up to 1 hour before dose) and 2 hours post dose (± 30 minutes).
- Symptom-directed physical examination pre-dose only
- Examination of injection site will be performed 1 hour (±30 min) pre-AGI-134 administration, 1 hour (±30 min) and 72 hours (±1 hour) post AGI-134 administration
- Vital signs (blood pressures, pulse rate, O2 saturation, oral temperature in °C, respiratory rate) will be assessed 1-hour pre-AGI-134 administration and 0.5, 1, 24, 36, 48 and 72 hrs post AGI-134 administration
- ECOG performance status
- Photography of superficial injected and non-injected lesions (if a different lesion is injected, the previous injected lesion should be photographed as well): 1 hour (±30 min) pre-AGI-134 administration and 1 hour (±30 min) and 72 hours (±1 hour) post AGI-134 administration
- Review general instructions before study drug administration (see section 5.7)

agalin A subsidiary of BIO		PRIVILEGED & CONFIDENTIAL
Investigational Product: AGI-134	A Phase I/IIa, multicentre, two-parts, open label study designed to evaluate the safety and tolerability of escalating	Protocol No. AGI-134.FIM.101
Phase: I/IIa	doses of AGI-134 in unresectable/metastatic solid tumours.	Version 6.1 31 May 2021

- AGI-134 administration (every effort should be made to inject the same lesion as in previous cycle)
- Blood will be drawn for:
  - PT/INR and aPTT (results should be available before injection)
  - o CBC with differential
  - Biochemistry panel
  - Blood for anti-Gal IgE pre-dose (if IgE anti-Gal is detected during assessment at Cycle 3, Cycle 4 dosing with AGI-134 will be cancelled)
  - o C5a pre-dose and 2 and 6 hours post AGI-134 administration
  - o Flow cytometry pre-dose and 24 hours post AGI-134 administration
  - o Cytokines pre-dose and 2, 6, 12 and 24 hours post AGI-134 administration
  - Anti-Gal antibodies IgG/IgM and sub classing pre-dose only
  - PBMC + cryopreservation pre-dose only
  - TCR Sequencing pre-dose only
  - RNA isolation (Gene expression/sequencing) 24 hours post AGI-134 administration
  - PK of AGI-134 and metabolites: up to 1 hour prior to AGI-134 administration and at 0.5, 1, 2, 4, 6, 8, 12, 24, 36, 48 and 72 hrs post AGI-134 administration.
     For detailed time window for sample collection refer to the Laboratory Manual.
- Biopsies should be performed prior to AGI-134 administration. If not done on the same day of AGI-134 administration, a window of -7 days prior AGI-134 administration is allowed. Two biopsies should be taken:
  - From the tumour lesion to be injected
  - From an un-injected lesion
- Tumour imaging assessment
- RECISTv.1.1 assessment or superficial lesion measurement according to the tumour type will be done on Cycle 3, during Week 9 (before injection of AGI-134 on Cycle 4 - Day 1).

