  - O Part 1: The total size of the tumour(s) should allow injection of the total volume required at each escalation cohort. The volume can be injected into one lesion or divided into more than one lesion, but the total volume should be given according to the total dose at each escalation part. When volume is divided between several tumours, at least 1 mL should be injected into each tumour.
  - o Part 2: Tumour dimensions should allow injection of a minimum of 1 mL.
- 8. Has  $\geq$  2 lesions
  - Has ≥1 injectable lesion which is amenable to injection and biopsy and is evaluable according to RECIST v1.1.
  - Has another lesion which is amenable for biopsy and is evaluable according to RECIST v1.1. Superficial large lesions of more than 25 cm can be considered as two lesions upon discussion with and approval by the Sponsor.
- 9. Evaluable Disease according to RECIST v1.1
- 10. Has an Eastern Cooperative Oncology Group (ECOG) Performance Status score of 0 or 1.
- 11. Has a life expectancy >3 months

		PRIVILEGED & CONFIDENTIAL
Investigational Product: AGI-134		Protocol No. AGI-134.FIM.101
Phase: I/IIa		Version 6.1 31 May 2021

- 12. Adequate organ function at Screening as defined below. All laboratory assessments should be performed within 10 days prior to treatment initiation.
  - o Haematology:
    - White blood cell (WBC)  $\geq 2,500/\text{mm}^3$
    - Absolute neutrophil count ≥ 1500 /mm^3
    - Platelet count  $\geq 100,000/\text{mm}^3$
    - Haemoglobin ≥9 g/dL or ≥5.6 mmol/L
    - Haematocrit >30%
  - Renal function:
    - Creatinine ≤1.5x Upper limit of normal (ULN) OR measured or calculated creatinine clearance (glomerular filtration rate [GFR]) can also be used in place of creatinine or CrCl) > 50 mL/min for subject with creatinine levels > 1.5x institutional ULN
  - o Hepatic function:
    - Total Bilirubin: ≤1.5xULN OR Direct bilirubin ≤ULN for subjects with total bilirubin levels >1.5xULN
    - AST (SGOT) and ALT (SGPT): ≤2.5xULN OR ≤5xULN for subjects with liver metastases
  - Coagulation
    - International Normalised Ratio (INR) or Prothrombin Time (PT): ≤1.5xULN unless subject is receiving anticoagulant therapy as long as PT or PTT is within therapeutic range of intended use of anticoagulants
    - Activated Partial Thromboplastin Time (aPTT): ≤1.5xULN unless subject is receiving anticoagulant therapy as long as PT or PTT is within therapeutic range of intended use of anticoagulants

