## **Termination / Early Termination Visit Procedures**

- · Review concomitant medications
- AEs Recording (AEs up to 30 days post last dose of study drug and SAEs up to 90 days post last dose of study drug)
- 12-lead electrocardiogram (ECG) local reading
- · Full physical examination
- Examination of injection site
- Vital signs (blood pressures, pulse rate, O2 saturation, oral temperature in °C, respiratory rate)
- Weight
- ECOG performance status
- Photography of all superficial injected lesions
- Blood will be drawn for:
  - o Pregnancy test in serum
  - o CBC with differential
  - o Biochemistry panel
  - o T3, free T4 and TSH
  - Flow cytometry
  - Anti-Gal antibodies IgG/IgM and sub classing
  - PBMC + cryopreservation
  - TCR Sequencing
  - RNA isolation (Gene expression/sequencing)
- In case Early Termination occurred prior to Cycle 3, every effort should be made to perform biopsies on the ET visit. Two biopsies should be taken:
  - From the tumour lesion to be injected
  - From the un-injected lesion

203		PRIVILEGED & CONFIDENTIAL
Investigational Product: AGI-134	A Phase I/IIa, multicentre, two-parts, open label study designed to evaluate the safety and tolerability of escalating	Protocol No. AGI-134.FIM.101
Phase: I/IIa	doses of AGI-134 in unresectable/metastatic solid tumours.	Version 6.1 31 May 2021

- Tumour Imaging Assessment will be required for termination visit at Week 54 or Early Termination visits, conducted ≥ 9 weeks from last imaging/ RECIST v 1.1 assessment.
- RECIST v 1.1 assessment will be done using imaging and/or superficial lesion measurement according to the tumour type. This assessment will be required for Termination visit at Week 54 or Early termination conducted ≥ 9 weeks from last imaging/ RECIST v 1.1 assessment. Post-Study Anti-Cancer Therapy Status (for early termination)
- Survival and disease status (for early termination)

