#### 5.12.2 Planned Biopsy Analysis

Biopsies will be performed at baseline and Cycle 3 from injected lesion as well as from uninjected lesion.

Additional biopsy from superficial injected lesion will be performed on Cycle 1 Day 3 (48-72 hours) post AGI-134 administration. This biopsy is mandatory for superficial injected lesions

VS		PRIVILEGED & CONFIDENTIAL
Investigational Product: AGI-134		Protocol No. AGI-134.FIM.101
Phase: I/IIa	doses of AGI-134 in unresectable/metastatic solid tumours.	Version 6.1 31 May 2021

and is also requested for deep lesions, unless not considered in the best interest for the patient by the PI.

Procedures, collection, storage and shipping instruction will be provided in the *Administration* of AGI-134 and Tumour Biopsy Procedures in Study AGI-134.FIM.101 document.

The reason for a missing biopsy assessment should be documented within the eCRF. All efforts should be done in order to conduct all the biopsy assessments as required in the protocol.

Two core biopsies are required to be taken at each timepoint and from each lesion. All biopsies will be processed as Formalin-Fixed Paraffine-Embedded (FFPE) blocks.

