	Visit	Visit		Cyc	cle 1	271	Cycle	Cycle	Cycle	Visits	Termination	Follow- up
Days	0	0	Day 1	Day 3	Day 8	Day 15	2	3	4		Visit/Early Termination Visit	
Weeks	0	0	1	1	2	3	4-6	7-9	10-12	18, 27, 36 & 45	54	Every 9 weeks
Scheduling Window (Days) unless specified otherwise	-28 to 0	-3 to Day 1 (Pre- dose)	0	±1	+3	+3	±3	±3	±3	±3	±3	±7
Urinalysis	X	X					X		X			
Central Laboratory 			8	·			>		W			8
Blood for Anti-Gal IgE	X							X 				
CH50			X 									
C5a			X 				X 	X 	X 			
Flow cytometry (FACS)			X 				X 	X 			X	
Cytokines			X 	X				X 				
Anti-Gal antibodies IgG/IgM			X		X		X 	X 	X 		X	
Anti-Gal sub classing			X 				X 	X 	X 		X	
PBMCs isolation + cryopreservation			X 	X			X 	X 			X	
HLA and MHCII haplotyping			X 									
DNA isolation (MSI/dMMR/TMB,WES) blood			X 									

agalin A subsidiary of B 10	IMUNE LINERX	PRIVILEGED & CONFIDENTIAL
Investigational Product: AGI-134	A Phase I/IIa, multicentre, two-parts, open label study designed to evaluate the safety and tolerability of escalating doses of AGI-134 in unresectable/metastatic solid tumours.	Protocol No. AGI-134.FIM.101
Phase: I/IIa		Version 6.1 31 May 2021

	Screening	Baseline					C	ore Study				Long-Term
	CONTRACTOR NO.	Visit	Visit Visit	t Cycle 1		Cycle Cycle Cy	Cycle	Cycle Visits	Termination	Follow- up		
Days		0	Day 1	Day 3	Day 8	Day 15	2 3	3	4		Visit/Early Termination Visit	
Weeks	0	0	1	1	2	3	4-6	7-9	10-12	18, 27, 36 & 45	54	Every 9 weeks
Scheduling Window (Days) unless specified otherwise	-28 to 0	-3 to Day 1 (Pre- dose)	0	±1	+3	+3	±3	±3	±3	±3	±3	±7
TCR Sequencing blood			X 					X 			X	
RNA isolation (Gene expression/sequencing) blood			X 	X				X 			X	
Blood for PK (AGI-134 and metabolites)			X 				X 	X 	X 			
Biopsies 				1				L				
Biopsy of injected lesion	*	X 		X 				X 			X 	
Biopsy for un-injected lesion		X 						X 			X 	7
Disease assessment								.				
Tumour Imaging 	X							X		X	X	
RECIST 1.1 assessment	X							X		X	X	

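### The Cycle 3 biopsy wording lets a never-treated lesion stand as the injected-lesion specimen when the lesion first changes at Cycle 3

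*Combined protocol and SAP*

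**What the plan says.** Two biopsies are due at Cycle 3. Section 5.3.4 (Cycle 3 Procedures) says "Biopsies should be performed prior to AGI-134 administration", with a window of up to 7 days before the dose. The first specimen is described as "From the tumour lesion to be injected" and the second as coming from a lesion that is un-injected. Section 5.2 uses the same phrase at Baseline, where it is correct because nothing has been injected yet. Section 5.4 uses it again for early termination before Cycle 3 ("In case Early Termination occurred prior to Cycle 3, every effort should be made to perform biopsies on the ET visit").

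On continuity of the treated lesion, section 5.3.4 says "every effort should be made to inject the same lesion as in previous cycle", with equivalent text at Cycles 2 and 4. The photography item covers a change: "if a different lesion is injected, the previous injected lesion should be photographed as well". No biopsy instruction matches it.

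Section 5.12.2 puts it differently: "Biopsies will be performed at baseline and Cycle 3 from injected lesion as well as from uninjected lesion". In Tables 6 and 7 the row is labelled "Biopsy of injected lesion" and is marked at Baseline as well as later.

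Table 3 schedules tissue histology/IHC and RNA at Baseline, Cycle 1 Day 3, Cycle 3 and Termination. Tissue T-cell receptor (TCR) sequencing is scheduled at Baseline, Cycle 3 and Termination only.

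**The concern.** A specimen meant to show what AGI-134 does inside a treated tumour should be chosen by the lesion's past exposure. At Cycle 3 the wording chooses it by the next injection. When the lesion stays the same, the two agree. When it first changes at Cycle 3, they do not: tissue with no exposure is labelled injected, and the lesion that received the earlier doses is not named for biopsy.

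The comparator has a matching gap. It need not be the lesion biopsied at Baseline, and nothing says it must never have been injected.

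The tissue data serve the secondary endpoints in section 2.2.2 on immune response, mechanism of action and biomarkers. A Baseline-to-Cycle 3 difference between two different lesions, the second untreated, says nothing about change on treatment. If exposure is not recorded with each specimen, the label may not be correctable later.

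**Working it through.** The plan states no sample size, power or rate of lesion change for the tissue analysis, so there is no figure to reproduce. The check is a reading of the rule, followed by an illustration.

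**What the rule samples.** Call the lesion injected at Cycle 1 A and another lesion B. The Cycle 3 biopsy precedes the third dose.

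| Injected at Cycles 1, 2, 3 | Lesion named at Cycle 3 | Doses it has had | Same as Baseline injected-lesion specimen? |
|---|---|---|---|
| A, A, A | A | 2 | yes |
| A, B, B | B | 1 | no, but treated |
| A, A, B | B | 0 | no, and untreated |

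Only the third row puts never-treated tissue under the injected label. The second row breaks the pairing but not the exposure.

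**Does other text settle it?** Section 5.12.2 and the table rows speak of the injected lesion, but they do so at Baseline too, when no lesion has been injected. The label must therefore cover a lesion still to be injected. None of these places ties the Cycle 3 specimen to the lesion biopsied at Baseline. In Part 2, section 3 allows one or more tumours to be injected, so the named lesion may not be unique either.

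**Part 1.** Table 6 places the Cycle 3 biopsies in the Day 8 column, with a footnote giving week 8. Table 7 shows Cycle 3 as weeks 7 to 9, so week 8 falls after the Cycle 3 dose. That conflicts with the pre-dose timing in section 5.3.4. The mechanism above is therefore clear only for Part 2.

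**Size (illustration).** Inputs: n of about 35 for Part 2 (section 8.1); q, the share whose lesion first changes at Cycle 3, is an assumption. Expected number = 35 × q. Chance of at least one = 1 − (1 − q)^35.

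| q | Expected of 35 | Chance of at least one |
|---|---|---|
| 5% | 1.75 | 83% |
| 10% | 3.5 | 97.5% |
| 20% | 7.0 | >99.9% |
| 30% | 10.5 | >99.9% |

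The figure of 35 is a ceiling, because subjects who leave before Cycle 3 have no Cycle 3 specimen.

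**Dilution (illustration).** Suppose untreated tissue shows no mean change and treated tissue a standardised mean change d. The observed mean is d(1 − q), with variance 1 + q(1 − q)d². For a two-sided 0.05 test (assumed; the plan's threshold is not visible), power = Φ(mean/SD × √n − 1.96). With n = 35 and d = 0.5:

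- q = 0: 0.5 × 5.916 − 1.96 = 0.998, power 84%
- q = 10%: 0.45/1.011 × 5.916 − 1.96 = 0.673, power 75%
- q = 20%: 0.40/1.020 × 5.916 − 1.96 = 0.361, power 64%

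A true effect in distant lesions would make the dilution smaller. Added variance from comparing two different lesions would lower power further. Neither is modelled.

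**The case against.** The strongest reply is that this is Baseline wording carried over by accident. The section devoted to biopsies and both schedules speak of the injected lesion, best effort keeps the lesion constant in most subjects, and lesion choice is delegated to a separate administration and biopsy procedures document that was not available for this review. That document may settle the matter, and so may the eCRF. Even so, the protocol's visit instruction gives the wrong specimen in a situation the protocol itself foresees, and the other sections do not override it.

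Two limits stand. Sections 5.3.2 and 5.12.2 require a Cycle 1 Day 3 biopsy of superficial injected lesions and request it for deep ones, so treated tissue for IHC and RNA usually exists whatever happens at Cycle 3. TCR sequencing does not have that cover. Blood markers (C5a, cytokines, flow cytometry, anti-Gal, blood TCR and RNA) also serve the same endpoints. It is also fair to say that taking a previously injected lesion as un-injected strains the words, though nothing rules it out.

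Three stronger readings are tempting but unsupported:

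- A reader might count every subject whose lesion changes at any time up to Cycle 3. A change at Cycle 2 leaves the new lesion already dosed by the Cycle 3 biopsy.
- A reader might infer that Part 1 forces the comparator to be injected, since its eligibility text says "the total volume should be given according to the total dose at each escalation part" and only two lesions are required. No passage says a second lesion must then be used, and Table 6 places that biopsy after the dose.
- A reader might take section 5.4 as directing an early-termination biopsy to an untreated lesion. No injection follows that visit, so the words have no referent; they are unclear rather than a wrong instruction.

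**Conclusion.** The point holds as a wording defect with a real consequence in a limited group: Part 2 subjects whose injected lesion first changes at Cycle 3. In them, the literal rule mislabels untreated tissue and leaves the treated lesion unsampled. The loose definition of the comparator is part of the same defect. The number affected is unknown; the counts and power figures above rest on assumed rates and an assumed test, and show only that a modest rate would matter.

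A reader might go further and infer that the best local responders lose their specimen, biasing the local effect toward nil. Injection volume does depend on tumour dimensions, so shrinkage is a plausible reason for a change, but no passage gives reasons for changing lesion. The direction of any bias is therefore not established. Nor does the visible text define a formal paired test: the study is single-arm, and section 8.2 gives mainly descriptive methods and defers detail to a SAP. What is weakened is supportive Baseline-to-Cycle 3 tissue evidence, most of all TCR sequencing.

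**What to change.** - **Section 5.3.4, Cycle 3:** specify the lesion already injected at earlier cycles and biopsied at Baseline. For the comparator, specify the same un-injected lesion biopsied at Baseline, provided it has never been injected.
- **Section 5.4:** correct the same phrase in the same way.
- **Section 5.12.2 and Tables 6 and 7:** state that after Baseline the injected lesion means this lesion. The phrase in section 5.3.4 does not occur in 5.12.2, so that section needs a clarification, not a replacement.
- **Part 1 timing:** reconcile week 8 in Table 6 with the pre-dose timing in section 5.3.4.
- **Data and analysis:** record the lesion identifier and number of prior injections for each specimen, and classify specimens by that history, including when more than one lesion is injected.

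The cost is wording, matching text in the biopsy procedures document, and two eCRF fields if they are not already there. No biopsies are added, and the choice of lesion to treat is untouched. In a subject with exactly two lesions who first changes at Cycle 3, the same two pre-dose biopsies would simply carry the right labels: A has had two doses and B none. The downside is a few missing pairs where the lesion biopsied at Baseline can no longer be sampled, or the comparator has since been injected.
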